#### 9.4.1.3. Categorical Endpoints

Differences between Arms A and B for ORR, CR and PR rates, nodal response rate, splenomegaly response rate, hepatomegaly response rate, ALC response rate, platelet response rate, hemoglobin response rate, and neutrophil response rate will be compared using Cochran-Mantel-Haenszel Chi-square tests for association between treatment and response, after adjusting for stratification factors. In the analyses of ORR, subjects who do not have sufficient baseline or on-study tumor assessment to characterize response will be counted as failures. For all analyses, odds ratios and the corresponding 95% CIs will be presented.

The potential influence of subject baseline characteristics and of treatment on response rates will be explored with logistic regression modeling.

#### 9.4.1.4. Continuous Endpoints

Differences between treatment arms for percentage changes in lymph node area and for changes in performance status, PI3K/AKT/mTOR pathway activation, and plasma chemokines/cytokines will be assessed using analysis of covariance (ANCOVA) with baseline values and stratification factors as covariates; in these analyses, both changes from baseline to each subsequent timepoint and best overall on-study changes will be compared. Least-squares means and 95% CI will be presented.

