### 9.3.2. Data Handling Conventions

#### 9.3.2.1. General Methods

By-subject listings will be created for important variables from each eCRF module. Summary tables for continuous variables will contain the following statistics: N (number in analysis set), n (number with data), mean, and standard deviation, 95% confidence intervals (CIs) on the mean, median, minimum, and maximum. Summary tables for categorical variables will include: N, n, percentage, and 95% CIs on the percentage. Unless otherwise indicated, 95% CIs for binary variables will be calculated using the binomial distribution (exact method) and will be 2-sided. Data will be described and summarized by relevant treatment arm, analysis set, and timepoint. As appropriate, changes from baseline to each subsequent timepoint will be described and summarized by treatment arm. Similarly, as appropriate, the best change from baseline during the study will also be described and summarized by treatment arm. Graphical techniques (eg, waterfall plots, Kaplan-Meier curves, line plots) may be used when such methods are appropriate and informative.

The baseline value used in each analysis will be the last (most recent) pre-treatment value. Subjects with discrepancies between the stratification factor values at randomization and the actual values as documented on data review will be categorized in the analyses according to the actual values. In the situation that there is insufficient information in a stratum (ie, if there are < 6 subjects or there is no informative event in a stratum), that stratum will be pooled with the smallest adjacent stratum for stratified analyses; the smallest stratum is defined as that stratum having the fewest number of subjects or the fewest number of events in case the former is a tie and the adjacent stratum is defined as a stratum having 2 factors of the 3 at the same level. Data from all sites will be pooled for all analyses. Analyses will be based upon the observed data unless methods for handling missing data are specified. If there is a significant degree of non-normality, analyses may be performed on log-transformed data or nonparametric tests may be applied, as appropriate.

Unless otherwise specified, all analyses will be 2-sided at the 0.05 level of significance.

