#### 9.4.1.5. Health-Related Quality of Life and Performance Status

The FACT-Leu questionnaire data will be scored, processed, and standardized (ranging from 0-100) according to the user manual. Missing items in a subscale will be imputed consistently with the user manual instructions. Data collected from the FACT-Leu instrument will not be reconciled with adverse event or laboratory data or with EQ-D5 findings.

The mean and change from baseline in mean scores to each subsequent assessment will be summarized for the FACT-Leu subscale and composite scores. The best change from baseline during the study, defined as the highest positive value among all post-baseline visits minus the baseline value, will also be summarized. Mixed-effects models will be used to assess the treatment effect on change from baseline over time.

The EQ-5D questionnaire data will be scored, processed, and standardized according to the user manual. U.S. preference-weighted index score computed using EQ-5D data {[Shaw 2005](#)} will be calculated. Change from baseline in EQ-5D visual analogue scale and EQ-5D index will be summarized and analyzed using mixed-effects models.

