### 9.5. Sample Size

Based on data from the Phase 2 pivotal study ofatumumab {[Wierda 2010](#)} and considering the population of subjects to be enrolled to this study, it is reasonable to assume that administration of ofatumumab to subjects with previously treated CLL in Arm B of this trial will result in a median PFS of ~8 months. An improvement in median PFS from 8 months to 14 months due to the addition of idelalisib to ofatumumab in Arm A of the study would correspond to a benefit ratio of 1.75 (hazard ratio 0.57).

It is assumed that PFS times are exponentially distributed in each of the 2 arms. With a hazard ratio equal to 1 under the null hypothesis of no difference between the 2 treatment arms and a hazard ratio of 0.57 under the alternative hypothesis of superiority of the idelalisib-containing combination, 129 events (definitive CLL progressions or deaths) are required to achieve a power of >0.85 based on a log-rank test with a 2-sided significance level of 0.05. Further assuming a planned accrual period of 12 months (with approximately half of the subjects enrolled during the initial 60% of the accrual period, and the remaining half of the subjects enrolled during the last 40% of the accrual period), a minimum follow-up period of 12 months, and an expectation that 10% of subjects will be lost to follow-up (5% during the accrual period and 5% during the follow-up period), and to ensure the primary analysis on PFS will be performed before or at the planned minimum 12-month follow-up period, 170 subjects will be enrolled into Arm A and 85 subjects will be enrolled into Arm B in order to achieve the expected number of events by the end of the planned minimum 12-month follow-up period. If the planned subject enrollment does not appear adequate to accrue the expected number of events within the proposed follow-up period, the sample size may be adjusted upward.

It is expected that there will be approximately 65 deaths at the time of final analysis. This would provide ~85% power to detect a HR of 0.45 for overall survival based on a log-rank test at 2-sided alpha level of 0.03.

The resulting safety data set provided by the idelalisib-treated subjects (N=170) compares favorably with the safety data set derived from the initial pivotal registration trials for ofatumumab (N=138) {[Wierda 2010](#)}, oral fludarabine (N=78) {[Boogaerts 2001](#)}, or alemtuzumab (N=93) {[Keating 2002a](#)}.

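### The exploratory ANCOVA of best on-study change has no common observation window, so it is modestly biased toward Arm A if the planned PFS benefit holds

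*Protocol*

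**What the plan says.** Protocol 9.4.1.4 applies ANCOVA, with baseline value and stratification factors as covariates, to "percentage changes in lymph node area and for changes in performance status, PI3K/AKT/mTOR pathway activation, and plasma chemokines/cytokines". For these measures, "both changes from baseline to each subsequent timepoint and best overall on-study changes will be compared". It sets no common window for the best change and makes no allowance for the number of assessments. Section 9.3.2.1 supplies the test level: "Unless otherwise specified, all analyses will be 2-sided at the 0.05 level of significance". Section 9.4.1.6 says p-values will be reported for the exploratory endpoints too, so this test will produce published p-values.

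Both arms follow the same visit schedule (Synopsis, Appendix 7). Under 5.9 and 7.3, subjects who stop study drug without progression stay on that schedule until progression or the end of participation. Section 9.5 plans for "An improvement in median PFS from 8 months to 14 months due to the addition of idelalisib".

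Section 9.4.1.5 treats HRQL differently. Best change, "defined as the highest positive value among all post-baseline visits minus the baseline value", is only summarized there, and treatment effect is assessed with mixed-effects models.

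**The concern.** The best of several noisy values is an extreme, and its expectation grows with the number of values. If idelalisib delays progression, Arm A subjects are assessed for longer and have more chances to record a favourable value. Baseline and stratification covariates cannot correct this, because the imbalance lies in the number of post-baseline values.

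When the primary hypothesis is true, the best-change comparison is therefore not a 5% test, and its error runs in one direction, toward the investigational arm. Effects on disease-associated biomarkers and on performance status are named objectives (3.2). A p-value that partly reflects time under observation could be read as pharmacodynamic activity or patient benefit.

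**Working it through.** **The plan's own figure.** The protocol gives no number for the best-change analysis, so its PFS assumptions were checked first. Section 9.5 states "a hazard ratio of 0.57 under the alternative hypothesis of superiority of the idelalisib-containing combination" and that "129 events (definitive CLL progressions or deaths) are required to achieve a power of >0.85"; the test there is two-sided at 5%. By Schoenfeld's formula with 2:1 allocation:

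- events = (1.960 + 1.036)² / [(2/3)(1/3)(ln 0.57)²] = 8.98 / (0.2222 × 0.3160) = 128
- power at 129 events = Φ(√(129 × 0.0702) − 1.960) = Φ(1.05) = 0.853

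The figure reproduces, so the 8 and 14 month medians can be used as the design's own.

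**Why an extreme drifts.** The expected maximum of K independent standard normal values is 0.85 for K = 3, 1.16 for K = 5, 1.42 for K = 8 and 1.63 for K = 12. With an intraclass correlation of 0.5, the within-subject SD is √0.5 = 0.71 of the total SD. Going from 3 to 5 values then moves the best value by about 0.71 × (1.16 − 0.85) = 0.22 SD with no change in the patient.

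**Simulation inputs from the protocol.** 170 and 85 subjects; exponential PFS with medians of 14 and 8 months; 12 months' accrual, half in the first 60% and half in the last 40%; 10% loss to follow-up (all 9.5). Scans at Weeks 8, 16, 24, 36 and 48, then every 12 weeks (Synopsis). Marker and performance-status visits as in Appendix 7.

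**Assumptions not in the protocol.** The within-subject correlation; unbounded noise with no trend; a 24-month cut-off (12 months' accrual plus 12 months' minimum follow-up), with 19.2 months as an earlier alternative because 9.5 expects the primary analysis at or before the minimum follow-up. Stratification factors were left out of the ANCOVA. There is no arm difference in the measure at any visit.

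**Results, 24-month cut-off, 3,000 trials per setting, correlation 0.5 and 0.7:**

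| Schedule | Mean assessments, A vs B | Shift toward A (SD) | Rejection at nominal 5% |
|---|---|---|---|
| Imaging | 4.5 vs 3.5 | 0.10, 0.08 | 15.7%, 13.1% |
| Markers | 10.3 vs 8.7 | 0.07, 0.06 | 11.7%, 10.6% |
| Performance status | 13.1 vs 11.5 | 0.06, 0.04 | 10.2%, 8.4% |

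Monte Carlo error near 10% is √(0.1 × 0.9 / 3000) = 0.5 percentage points. Over correlations of 0.4-0.8 and cut-offs of 19-24 months, rejection is roughly 7-12% for markers and performance status and 9-19% for imaging, with shifts of about 0.03-0.12 SD.

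**Controls.** With equal PFS in both arms, best change rejects in 4.3-5.4% of trials. Change at a single fixed visit (Week 24) rejects in 4.1-5.7%. The excess therefore comes from unequal follow-up combined with taking the extreme.

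**Sensitivity to the noise model.**

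- Serially correlated noise (decay of 12 or 26 weeks, correlation 0.5-0.7, 24-month cut-off) raises the rate to about 19-22% for markers and performance status and 16-17% for imaging.
- Karnofsky scores rounded to steps of 10 and capped at 100 (assumed mean 85-90) give about 7-9%, with a shift of 0.2-0.5 points.
- A floor on pathway activation gives about 6-7% and almost no shift.
- An identical early nodal fall and regrowth in both arms gives 7-11% at 19.2 months and 7-12% at 24.

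**Common windows.** At correlation 0.5, best change through Week 24 still rejects in 7.2-8.2%, because early progression already differs between arms. Through Week 16 it rejects in 5.4-6.0%, and through Day 78 (Week 12) in 5-7%.

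**The case against.** Several points on the other side stand. These endpoints are exploratory (9.2.2) and lie outside the sequential testing of 9.4.1.6, and 9.4.1.4 pairs best change with comparisons at each timepoint. The shift is small, and its size rests on a correlation the protocol does not give.

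A flat-noise model also suits some of the measures poorly. Section 3.5.1 places nodal responses within the first 16 weeks, so nodal best change is largely an early nadir. Progression is itself defined largely by nodal growth (7.5.4), which strains the idea of a PFS benefit with no nodal effect. The Karnofsky scale has a ceiling (Appendix 3), and 1.3.5.2.1 reports phosphorylated AKT at background after one week. Each of these shrinks the bias, and the imaging figure is best read as an upper-end scenario.

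A reader might infer that the HRQL analysis in 9.4.1.5 shares the defect. The documents do not support that: best change is descriptive there and inference uses mixed-effects models. A reader might also infer that the comparison will generally produce false effects. It will not, since most null trials still show no significant difference.

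The argument that the window is a detail for the statistical analysis plan does not succeed. The protocol already commits to testing the unrestricted best change, and that stated rule creates the bias.

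**Conclusion.** The point holds as a minor one, confined to the best-change test in 9.4.1.4. If the planned PFS difference materialises, the nominal 5% test has a true level of roughly 7-12% for markers and performance status. For node area it is about 9-19% under trendless noise. The shift of about 0.03-0.12 SD favours Arm A.

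These ranges assume exchangeable noise, an intraclass correlation of 0.4-0.8 and a cut-off of 19-24 months. Serial correlation would raise them; bounds and early nadirs would lower them. If PFS is equal in the two arms, the bias disappears. The primary and sequentially tested endpoints are not affected, and 9.4.1.5 needs no change.

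**What to change.** In 9.4.1.4, limit the between-arm ANCOVA tests to change at the scheduled timepoints, which are already planned. Give weight to early visits, when most subjects in both arms are still being assessed; late visits compare only those who remain. Present best change by arm descriptively, using the summaries and waterfall plots that 9.3.2.1 already provides for.

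If a best-change test is kept, restrict it to a short common window: for example, through Week 12 for markers and performance status, and through Week 16 for node area. A Week 12 window would hold only the Week 8 scan, whereas Week 16 gives two. A window through Week 24 is too long to restore the nominal level.

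The cost is a wording change in one section and, if the test is dropped, one exploratory p-value per measure. No data collection changes.

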#### 9.4.1.5. Health-Related Quality of Life and Performance Status

The FACT-Leu questionnaire data will be scored, processed, and standardized (ranging from 0-100) according to the user manual. Missing items in a subscale will be imputed consistently with the user manual instructions. Data collected from the FACT-Leu instrument will not be reconciled with adverse event or laboratory data or with EQ-D5 findings.

The mean and change from baseline in mean scores to each subsequent assessment will be summarized for the FACT-Leu subscale and composite scores. The best change from baseline during the study, defined as the highest positive value among all post-baseline visits minus the baseline value, will also be summarized. Mixed-effects models will be used to assess the treatment effect on change from baseline over time.

The EQ-5D questionnaire data will be scored, processed, and standardized according to the user manual. U.S. preference-weighted index score computed using EQ-5D data {[Shaw 2005](#)} will be calculated. Change from baseline in EQ-5D visual analogue scale and EQ-5D index will be summarized and analyzed using mixed-effects models.

#### 9.4.1.6. Control of Type I Error Rate in Efficacy Analyses

In the efficacy analyses, the following procedures will be implemented to preserve the overall type I error rate across the primary and secondary endpoints of the study at a 2-sided significance level of 0.05.

The primary endpoint analysis will serve as the gatekeeper for the secondary endpoint analyses, ie, the primary efficacy hypothesis must be made before the efficacy hypotheses for the secondary efficacy endpoints can be tested. The secondary endpoints will be the following:

- ORR
- Lymphadenopathy node response rate
- CR rate
- OS
- PFS in the subgroup of subjects with 17p deletion and/or TP53 mutation

If the primary hypothesis is rejected, the 5 secondary endpoints will be sequentially tested at the 2-sided 0.03 significance level in the order listed above. If a null hypothesis is not rejected, formal sequential testing will be stopped and only nominal significance will be cited for the remaining secondary endpoints. Analyses and p-values will be reported for all the efficacy endpoints, including the primary endpoint, the secondary endpoints, and all of the exploratory endpoints.

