**Criteria for Evaluation:**

Primary Endpoint

- Progression-free survival (PFS) – defined as the interval from randomization to the earlier of the first documentation of definitive disease progression or death from any cause; definitive disease progression is CLL progression based on standard criteria, other than lymphocytosis alone

Secondary and Exploratory Endpoints

- Five endpoints are designated as secondary endpoints for which sequential testing will be performed to control Type I error rate. Secondary endpoints will be ORR, lymph node response rate, OS, PFS in the subgroup of 17p deleted and/or TP53 mutated subjects, and CR rate. All other endpoints will be considered exploratory.

*Tumor Control*

- Overall response rate (ORR) – defined as the proportion of subjects who achieve a complete response (CR) or partial response (PR) response for at least 8 weeks
- Lymph node response rate – defined as the proportion of subjects who achieve a  $\geq 50\%$  decrease from baseline in the sum of the products of the greatest perpendicular diameters (SPD) of index lesions
- PFS in the subgroup of subjects with 17p deletion and/or TP53 mutation
- CR rate – defined as the proportion of subjects who achieve a confirmed CR

■ [REDACTED]

■ [REDACTED]

■ [REDACTED]

[REDACTED]

[REDACTED]

[REDACTED]

[REDACTED]

[REDACTED]

[REDACTED]

[REDACTED]

*Patient Well-Being*

- Overall survival (OS) – defined as the interval from randomization to death from any cause

[REDACTED]

[REDACTED]

*Pharmacodynamic Markers of Drug Activity and Resistance*

[REDACTED]

*Exposure*

[REDACTED]

*Safety*

[REDACTED]

*Pharmacoeconomics*

[REDACTED]

---

**Statistical Methods:** Analysis Methods

Appropriate data analysis sets will be defined. The intent-to-treat (ITT) analysis set will be used in the analyses of the primary efficacy endpoint, PFS. The ITT analysis set will include data from all subjects who are randomized, with study drug assignment designated according to initial randomization, regardless of whether subjects receive any study drug(s) or receive a different regimen from that to which they were randomized. A safety analysis set will comprise data from subjects who receive  $\geq 1$  dose of study drug, with treatment assignment designated according to the actual study drug(s) received. Other analysis sets [per-protocol (PP) and pharmacodynamic/pharmacokinetic analysis sets] will be used for certain analyses as well.

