Subject characteristics and study results will be described and summarized by treatment arm and assessment for the relevant analysis sets. Descriptive summaries will be prepared to show sample size, mean, standard deviation, 95% confidence intervals (CIs) on the mean, median, minimum, and maximum for continuous variables and counts, percentages, and 95% CIs on the percentage for categorical variables.

An independent review committee (IRC) will review radiographic data and pertinent clinical data in order to provide expert evaluation of tumor status. The findings of the IRC will be considered primary for analyses of PFS and other tumor control endpoints.

For the primary efficacy analysis, the difference in PFS between the treatment arms will be assessed in the ITT analysis set using Kaplan-Meier methods and the stratified log-rank test. Medians, ranges, the proportions of subjects who are progression-free at 24 and 48 weeks from randomization (based on Kaplan-Meier estimates), hazard ratios, and the corresponding 95% CIs (as calculated using a Cox proportional hazards regression model) will be presented.

Secondary endpoints will be ORR, lymph node response rate, OS, PFS in the subgroup of subjects with 17p deletion and/or TP53 mutation, and CR rate. The primary efficacy hypothesis relating to PFS must be rejected at the pre-specified significance level before the efficacy hypotheses for these secondary efficacy endpoints are tested. These 5 secondary endpoints will be tested at the 2-sided 0.03 significance level in the order listed at an interim or final analysis when the primary endpoint is rejected. If a null hypothesis is not rejected, formal sequential testing will be stopped and only nominal significance will be cited for the remaining secondary endpoints.

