#### 1.3.5.2.2. Phase 1 Combination Study in Patients with Hematological Malignancies

A separate Phase 1 trial (Study 101-07) has evaluated the safety and preliminary activity of idelalisib given in combination with ofatumumab to subjects with recurrent CLL {[Barrientos 2012](#), [Furman 2012](#)}.

In this study, idelalisib (150 mg BID) was co-administered with a total of 12 infusions of ofatumumab given over 24 weeks (300-mg initial dose followed 1 week later by 1,000 mg weekly for 7 doses, followed 4 weeks later by 1,000 mg every 4 weeks for 4 doses). Thereafter, subjects continued to receive single-agent idelalisib as long as the subject was safely benefiting from therapy. Subjects were evaluated in 4-week cycles; response and progression assessments were based on standard criteria {[Hallek 2008](#)}.

At the time of the data analysis, accrual of the cohorts was complete with 21 subjects enrolled and evaluable. Median [range] age was 66 [43-79] years. The majority (14/21; 67%) of patients had bulky adenopathy ( $\geq 1$  lymph node  $\geq 5$  cm in diameter). The median [range] number of prior therapies was 3 [1-6], including prior exposure to alkylating agents (18/21; 86%), rituximab (20/21; 95%), purine analogs (16/21; 76%), alemtuzumab (4/21; 19%), and/or ofatumumab (3/21; 14%). The median [range] idelalisib treatment duration was 36+ [0-48+] week.

No idelalisib-related dose-limiting toxicities were observed within the tested subject cohorts. Ofatumumab infusion reactions were manageable. One patient developed corticosteroid-related hyperglycemia and sepsis. No clinically significant myelosuppression was observed.

Almost all subjects (17/21, 84%) experienced marked and rapid reductions in lymphadenopathy within the first 2 cycles. The lymphocyte mobilization that is expected with PI3K $\delta$  inhibition was significantly reduced in magnitude and duration and persisted past Cycle 1 in only 1 patient. The ORR was 16/21 (76%) with 2/21 (10%) subjects showing evidence of complete response (CR), as reported by the investigators. Elevated baseline levels of CCL3, CCL4, CXCL13, and TNF $\alpha$  were significantly reduced after 28 days of treatment. At the time of the data analysis, overall PFS through 48 weeks was >75% and a median PFS had not yet been observed.

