#### **3.4. Secondary and Exploratory Endpoints**

The following secondary and exploratory endpoints will be defined and analyzed in this study. Five endpoints are designated as secondary endpoints for which sequential testing will be performed to control Type I error rate (see Section 9.4.1.6). Secondary endpoints will be ORR, lymphadenopathy response rate, OS, PFS in the subgroup of subjects with 17p deletion and/or TP53 mutation, and CR rate. All other endpoints will be considered exploratory.

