#### **9.2.2. Secondary and Exploratory Endpoints**

The secondary and exploratory endpoints of the study are defined in Section 3.4, grouped in categories relating to tumor control, patient well-being, pharmacodynamic markers of drug activity and resistance, exposure, safety, and pharmacoeconomics.

Of these endpoints, 5 endpoints are designated as secondary endpoints for which sequential testing will be performed to control Type I error rate (see Section 9.4.1.6). These secondary endpoints will be ORR, lymphadenopathy node response rate, OS, PFS in the subgroup of subjects with 17p deletion and/or TP53 mutation, and CR rate. Other endpoints will be considered exploratory.

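### The synopsis and Section 9.4.1.6 fix different test orders for the five secondary endpoints, so a missed CR test blocks a formal OS claim under one and not the other

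*Protocol*

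**What the plan says.** Two places prescribe a test order.

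- **Section 9.4.1.6 (Control of Type I Error Rate).** A bulleted list gives ORR, node response rate, CR rate, OS, then PFS in the 17p/TP53 subgroup. The text below it says that, once the primary hypothesis is rejected, "the 5 secondary endpoints will be sequentially tested at the 2-sided 0.03 significance level in the order listed above".
- **Synopsis, Statistical Methods.** The list is "ORR, lymph node response rate, OS, PFS in the subgroup of subjects with 17p deletion and/or TP53 mutation, and CR rate". These are tested, also at 2-sided 0.03, "in the order listed at an interim or final analysis when the primary endpoint is rejected".

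Both apply the same stopping rule: after a null hypothesis is not rejected, "formal sequential testing will be stopped and only nominal significance will be cited for the remaining secondary endpoints".

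Three other places name the same five endpoints without prescribing an order: the synopsis under Criteria for Evaluation ("Secondary endpoints will be ORR, lymph node response rate, OS, PFS in the subgroup of 17p deleted and/or TP53 mutated subjects, and CR rate"), Section 3.4, and Section 9.2.2 ("ORR, lymphadenopathy node response rate, OS, PFS in the subgroup of subjects with 17p deletion and/or TP53 mutation, and CR rate"). All three put CR rate last. Sections 3.4 and 9.2.2 send the reader to Section 9.4.1.6 for the sequential procedure.

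**The concern.** In a fixed-sequence procedure the order is the multiplicity rule, because it decides which hypotheses are tested at all. Here two incompatible orders are both current text.

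The difference is confined to CR rate, but CR rate sits on the path to OS in one order and not in the other. Suppose PFS, ORR and node response succeed, CR gives p > 0.03 and OS gives p < 0.03. The synopsis then supports a formal OS claim. Section 9.4.1.6 stops at CR, and OS carries only a nominal p-value. The same applies to PFS in the 17p/TP53 subgroup, which comes after OS in both lists.

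On the question of order, either list is a legitimate fixed sequence if it is the only one and is fixed in advance. Having two means that the order is not fixed.

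**Working it through.** **1. The two orders side by side**

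| Step | Synopsis, Statistical Methods | Section 9.4.1.6 |
|---|---|---|
| 1 | ORR | ORR |
| 2 | Node response rate | Node response rate |
| 3 | OS | CR rate |
| 4 | PFS, 17p/TP53 subgroup | OS |
| 5 | CR rate | PFS, 17p/TP53 subgroup |

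Steps 1 and 2 agree, and OS precedes subgroup PFS in both. CR rate moves from fifth to third. Both lists are complete and each has its own order sentence, so this is not an artefact of text extraction. The finding rests on this comparison alone; the rest shows what it could cost.

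**2. Inputs for the size**

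- Arm sizes 170 and 85, from Section 9.5; 2-sided level 0.03, so z = 2.170.
- OS: about 65 deaths, HR 0.45, 2-sided 0.03, from Section 9.5.
- Arm A CR rate: no design assumption is given. The only combination figure is in Section 1.3.5.2.2, "2/21 (10%) subjects showing evidence of complete response (CR), as reported by the investigators". Its exact 95% CI is 1.2% to 30.4%. It is single-arm, whereas IRC findings are primary in this trial.
- Arm B CR rate: not given, assumed 0% to 5%.

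**3. The plan's OS power**

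The Schoenfeld formula with 2:1 allocation gives Φ(√(65 × 2/9) × |ln 0.45| − 2.170) = Φ(3.801 × 0.799 − 2.170) = Φ(0.865) = 80.6%. Freedman's formula at 2:1 gives 87.1%. The protocol's figure of about 85% lies between them. I use 80.6% below; the choice does not affect the argument.

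**4. Power of the CR test and its effect on OS**

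CR power is by exact binomial enumeration of the unstratified pooled z-test, with Arm A at 10%. Blocking is 1 − CR power. The last row is CR power × 0.806. It takes CR and OS as independent and ORR and node response as already rejected.

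| Arm B CR rate | 0% | 1% | 2% | 3% | 4% | 5% |
|---|---|---|---|---|---|---|
| CR power | 98% | 81% | 60% | 42% | 28% | 17% |
| OS test blocked under 9.4.1.6 | 2% | 19% | 40% | 58% | 72% | 83% |
| Formal OS claim under 9.4.1.6 | 79% | 65% | 49% | 34% | 22% | 14% |

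Under the synopsis order OS does not wait for CR, so the corresponding chance of a formal OS claim is 81% throughout.

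**5. Sensitivity to the Arm A rate**

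Same method, Arm B from 0% to 5%:

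- Arm A 5%: CR power is at most 35%, and below 5% once Arm B reaches 3%.
- Arm A 15%: from nearly 100% down to 59%.
- Arm A 20%: from nearly 100% down to 90%.
- Arm A 30%: about 100% throughout.

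Blocking of the OS test therefore runs from near 0% to above 90% across plausible inputs.

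**The case against.** **Section 9.4.1.6 is the operative text.** It is the section devoted to type I error, and Sections 3.4 and 9.2.2 refer to it, so the synopsis could be read as a summary that was not updated. This has some weight, but no precedence rule is stated. The two sections that point to 9.4.1.6 themselves list CR rate last, so CR is last in four places and third in one. The cross-references do not show which order was intended.

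**The SAP may settle it.** It may, but the protocol does not leave the order open. It fixes it twice, so any SAP would have to contradict one of the two passages.

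**The size is soft.** This is correct. It rests on 2 of 21 patients and an assumed control rate, and the full range runs from negligible to decisive. The OS figures also assume the 65 deaths expected at the final analysis. The synopsis allows secondary testing at an interim, when fewer deaths are likely. The contradiction depends on none of this.

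**Type I error is not inflated as written.** Also correct. If the order were picked after seeing data, the false-claim chance at that step could reach 1 − 0.97² = 5.9% instead of 3%, with CR and OS both null and independent. Nothing in the protocol permits that choice, so I give it no weight in the conclusion.

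**The harm is limited.** The primary PFS test, ORR, node response, the 0.03 level and the stopping rule are unaffected, and Section 9.4.1.6 has p-values reported for every endpoint. What is at stake is the formal status of the OS, subgroup PFS and CR claims.

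**Conclusion.** The concern holds: the protocol is wrong as written and this must be corrected. Two current passages prescribe incompatible test orders, and the conflict decides whether OS and 17p/TP53 PFS can be formally claimed when CR misses 0.03.

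The practical size cannot be fixed from the protocol, because it gives no design CR rates for either arm. The table for Arm A at 10% is an illustration; other Arm A rates move the result across almost the whole scale. The existence of the conflict and the need to resolve it rest on the text alone.

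**What to change.** Choose one order and state it identically in both synopsis locations (Criteria for Evaluation and Statistical Methods) and in Sections 3.4, 9.2.2 and 9.4.1.6. Any SAP should carry the same order. Either order can serve. The sponsor should note that placing OS ahead of CR removes the dependence of the OS test on the CR result, and that CR power is uncertain on the protocol's own evidence.

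Do this before the first interim efficacy analysis, since the synopsis allows the secondary endpoints to be tested there. The protocol does not show whether an interim has already taken place. If one has, the order should be set by people who have seen no comparative results, with the date and their state of knowledge recorded. That record matters more here because, under Section 2.2, the sponsor's study team knows individual treatment assignments.

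The cost is a text amendment, with no effect on patients, data collection or sample size.
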